8.3 Partial or Missing Dates

The following conventions will be used to impute missing portions of dates for adverse events and concomitant medications. Note that the imputed values outlined here may not always provide the most conservative date. In those circumstances, the imputed value may be replaced by a date that will lead to a more conservative analysis.

A. Start Dates

- 1) If the year is unknown, then the date will not be imputed and will be assigned a missing value.
- 2) If the month is unknown, then:
 - i) If the year matches the first dose date year, then impute the month and day of the first dose date.
 - ii) Otherwise, assign 'January.'
- 3) If the day is unknown, then:
 - i) If the month and year match the first dose date month and year, then impute the day of the first dose date.
 - ii) Otherwise, assign the first day of the month.

B. Stop Dates

- 1) If the year is unknown, then the date will not be imputed and will be assigned a missing value.
- 2) If the month is unknown, then assign 'December.'
- 3) If the day is unknown, then assign the last day of the month.

8.4 Protocol Deviations

All protocol deviations will be included as a categorized listing. Safety and Intent to Treat analyses will include all enrolled subjects with all available data. Subjects with major deviations will be excluded from the per protocol analyses. Major deviations will be defined as anyone who completes through the primary endpoint and anyone who was enrolled but found to not meet inclusion/exclusion criteria during the course of the study. The number of subjects in each protocol deviation category listed below will be summarized by MDMA group, and individual subjects will be listed in the appendix.

Possible protocol deviations include the following seven categories:

- Subject entered study but did not meet criteria
- Subject developed withdrawal criteria but was not withdrawn
- Subject received excluded concomitant treatment
- Protocol procedure not performed per protocol
- Subject received incorrect treatment or incorrect dose
- Protocol procedure performed out of range
- Miscellaneous

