5.4 Removal of Subjects from the Study

Subjects can withdraw consent at any time without prejudice. The therapists can withdraw a subject if, in their clinical judgment, it is in the best interest of the subject or if the subject cannot comply with elements of the protocol that are critical for safety or for the scientific integrity of the study. If the therapists withdraw a subject from the study, the therapists will explain the reason for withdrawing the subject. The reason for early termination will be recorded in the subject's Source Records and CRF.

If a subject develops any exclusion criteria that in the opinion of the Medical Monitor, affects the safety of the subject, including psychiatric diagnosis, pregnancy, or requiring use of excluded medications, the subject will discontinue treatment but remain in the study for follow-up purposes. Whenever possible, the tests and evaluations listed for the follow-up will be carried out. Efforts will be made to obtain information about AE outcomes, if deemed necessary by the PI, Data Safety Monitor, Medical Monitor, and/or sponsor.

Subjects discontinuing treatment before the first experimental session will be replaced until blinded data has been collected from 12 subjects. Subjects who discontinue participation after the first experimental session will not be replaced, and an intent-to-treat analysis will be conducted with all available data. Subjects discontinuing treatment prior to the second experimental session will be asked to complete integrative therapy sessions, outcome assessments prior to discontinuation and complete the six-month follow-up assessment if possible. The blind will not be broken for these subjects until after the six-month follow-up assessments have been completed.

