Biomarkers will be evaluated for predictive and prognostic power. Separate estimates of effect size will be performed for OT, AVP and CORT. Changes in biomarker concentrations from pre-treatment levels will be used to analyze effects of acute dosing and to determine the time-course of elevated OT and AVP levels post-drug. Pre-treatment biomarker concentrations will be evaluated for predictive power using an exploratory hierarchical regression analysis with condition assignment in Stage 1 and biomarker concentrations at baseline as predictors and treatment outcomes as dependent variables. One regression will be performed with biomarker values taken at the second experimental session. A second regression will be performed on biomarker values taken two weeks after the second experimental session.

TAS-20 scores will be evaluated for predictive power using an exploratory hierarchical regression analysis with condition assignment in Stage 1 and TAS-20 scores at baseline as predictors and with LSAS scores as dependent measures. One regression will examine the predictive power of condition and baseline TAS-20 scores upon LSAS scores one month after the first experimental session and the other will investigate whether condition and baseline TAS-20 and will predict LSAS score at one month after the second experimental session.

Subjects who discontinue treatment prior to the second experimental session will be asked to complete the final outcome assessment prior to continuing to the 6-month follow-up whenever possible. The data from these subjects will be tested for equivalence to data from subjects completing the study per protocol. If found to be equivalent, data from these subjects will be combined for an exploratory intent-to-treat effect size estimate to examine results without bias towards subjects more likely to complete the study per protocol.

Stage 1 and Stage 2 outcomes in extension subjects will be compared after the outcome measure assessments are complete for all extension subjects.

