2.0 Introduction

This document presents a Statistical Analysis Plan (SAP) for MAPS study protocol MAA-1, a Phase 2 pilot clinical trial designed to evaluate the safety, feasibility, and efficacy of MDMA-assisted psychotherapy in treating social anxiety in adults on the autism spectrum.

The Multidisciplinary Association for Psychedelic Studies (MAPS) is a non-profit research and educational organization working to obtain approval for the prescription use of 3,4-methylenedioxymethamphetamine (MDMA)-assisted psychotherapy in adults on the autism spectrum with social anxiety. This is an initial pilot study to assess the efficacy of MDMA for this indication, following promising results from MAPS-sponsored studies of MDMA-assisted psychotherapy for posttraumatic stress disorder (PTSD).

The Phase 2 pilot study will examine the safety, feasibility, and efficacy of MDMA-assisted psychotherapy for social anxiety in 12 MDMA-naïve adults on the autism spectrum. This study is designed as a dose escalation study to assist with the exploration of safety and finding the most effective dose in this population. Subjects assigned to the MDMA group will receive two of three different doses, either 75 mg, 100 mg, or 125 mg MDMA. Overall, eight subjects (66.7%) will be randomized to the MDMA group and four subjects (33.3%) will be randomized to the placebo group. Subjects who received the placebo during Stage 1 will have the opportunity to cross over and take part in a second study segment, referred to as Stage 2, with two open-label experimental sessions, after completing the six-month follow-up visit at the end of Stage 1.

This study is designed to obtain safety data, and secondarily estimates of effect size for efficacy. The data will be used to determine study design and dosing for future studies for this indication. MAA-1 is also intended to contribute to the development of a manualized psychotherapeutic approach to this potential treatment. This study is exploratory. As a result, the sponsor will perform tests on all statistical comparisons without correcting for multiple comparisons.

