8.1 Analysis Populations

Intent-to-treat (ITT): all subjects who were randomized

Per protocol (PP): all subjects who completed Stage 1, underwent assessment of anxiety symptoms, and did not experience a major protocol deviation

Crossover: all subjects who completed Stage 2 in addition to completing Stage 1

Safety: all subjects who receive any study treatment

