8.10.2.1 Secondary Efficacy Analyses at Secondary Endpoints

Crossover Subject Analyses

LSAS data from subjects assigned to the placebo group, i.e. ‘crossover population,’ will be analyzed by t-tests on difference scores from Stage 1 endpoint (Visit 13) to Stage 2 endpoint (Visit 22) only if there is sufficient data to examine.

6-month Follow-up Analyses

To determine durability of effects, LSAS data will be analyzed by t-tests on difference scores from Stage 1 endpoint (Visit 13) to 6-month follow-up. Additionally, the following measures’ scores will be analyzed in this same fashion: PSS, BDI-II, IRI, RSES, STAI, TASIT, TAS-20, ERQ, QoL-Q

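### The SAP's per-protocol set is empty as written, and protocol 12.0 makes its exploratory intent-to-treat estimate depend on an undefined equivalence test that protocol 5.4 and the SAP do not have

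*SAP*

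**What the plan says.** **Per protocol.** SAP 8.1 defines the set as "all subjects who completed Stage 1, underwent assessment of anxiety symptoms, and did not experience a major protocol deviation". SAP 8.4 excludes subjects with major deviations from per-protocol analyses and gives major deviations two limbs. The first is "Major deviations will be defined as anyone who completes through the primary endpoint"; the second covers subjects enrolled but later found ineligible. SAP 8.10.1 puts the primary endpoint at Visit 13. SAP 8.7 requires disposition and dosing tables for the per-protocol population.

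**Early stoppers.** Protocol 5.4 replaces subjects who stop before session 1. For those who stop later it does not, and says "an intent-to-treat analysis will be conducted with all available data". Protocol 12.0 takes up subjects who stop before session 2: "The data from these subjects will be tested for equivalence to data from subjects completing the study per protocol". It continues: "If found to be equivalent, data from these subjects will be combined for an exploratory intent-to-treat effect size estimate", with the stated aim "to examine results without bias towards subjects more likely to complete the study per protocol".

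**Intent to treat and safety.** SAP 8.1 defines these as all randomised subjects and all treated subjects. SAP 8.4 says both analyses include all enrolled subjects. SAP 8.10.1 names no analysis set for the primary LSAS comparison.

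**The concern.** Completing through the primary endpoint is what a per-protocol subject should do, yet SAP 8.4 makes it the ground for exclusion. Followed literally, the required per-protocol tables have no subjects. Whoever corrects this while programming the tables is supplying a rule that the plan should state.

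The equivalence condition works against its own purpose. An intent-to-treat estimate matters most when stoppers differ from completers, and that is when the condition tends to withhold it. The trial is small and protocol 12.0 says effect sizes will set the sample size of later studies, so which subjects enter an estimate should not turn on an unstated test.

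**Working it through.** The documents give no per-protocol count, equivalence margin or dropout rate, so there is no stated figure to reproduce.

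**1. Per-protocol set.**

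- Membership (SAP 8.1) = completed Stage 1, anxiety assessed, no major deviation.
- Major deviation (SAP 8.4, as written) = completed through Visit 13, or found ineligible.
- Completing Stage 1 implies reaching Visit 13, whether Stage 1 ends at Visit 13 or at the six-month visit.
- Every subject who meets the first condition therefore fails the third: 0 of 12, whatever the dropout.

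With the negation restored, and assuming no ineligible subjects and complete anxiety assessments, the set is 12, 11, 10 or 9 subjects for 0, 1, 2 or 3 early stoppers.

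**2. Equivalence condition.** From the documents: 12 subjects. Assumed, because the documents are silent: 1 or 2 stoppers, normal data with equal SDs, all differences in SD units, and one of two candidate rules.

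- *Rule A*, two one-sided t-tests at 5% with margin M: pool if |observed difference| + t(0.95; 10) × s × SE < M, where s is the sample SD divided by the true SD.
- *Rule B*, pool if a two-sided 5% t-test is not significant.

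For 2 against 10:

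- SE = √(1/2 + 1/10) = 0.775.
- At s = 1 the 90% confidence interval half-width is 1.812 × 0.775 = 1.40 SD. With a 1 SD margin, even an observed difference of zero fails unless the sample SD is below 1/1.40 = 0.71 of the true SD.
- Under Rule B, a true 1 SD difference gives noncentrality 1/0.775 = 1.29 on 10 df and power 21.5%, so pooling occurs in 78.5%.

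For 1 against 11, SE = √(1 + 1/11) = 1.044 and the half-width is 1.89 SD.

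Chance of pooling (Rule A integrated over the distribution of the pooled SD; Rule B from the noncentral t):

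| Rule | Stoppers v completers | True difference 0 | 1 SD | 2 SD |
|---|---|---|---|---|
| A, margin 1 SD | 2 v 10 | 1.5% | 0.7% | 0.1% |
| A, margin 1.5 SD | 2 v 10 | 19.6% | 9.3% | 1.0% |
| A, margin 2 SD | 2 v 10 | 55% | 31% | 4.9% |
| B | 2 v 10 | 95.0% | 78.5% | 35.6% |
| A, margin 1 SD | 1 v 11 | 0.1% | 0.1% | 0.0% |
| A, margin 1.5 SD | 1 v 11 | 3.3% | 2.1% | 0.6% |
| A, margin 2 SD | 1 v 11 | 18.6% | 12.3% | 3.6% |
| B | 1 v 11 | 95.0% | 86.0% | 59.0% |

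For the same data-generating truth, the unstated rule largely decides whether the estimate exists. Within any one rule, pooling becomes less likely as stoppers differ more from completers.

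**3. Unnamed primary set.** Two kinds of subject can have a Visit 13 LSAS and still fall in one set but not the other. Early stoppers are asked for the final outcome assessment (protocol 5.4 and 12.0), and subjects found ineligible may have been assessed at Visit 13. One subject is 1/8 = 12.5% of the MDMA arm or 1/4 = 25% of the placebo arm.

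**The case against.** The per-protocol error is an obvious slip. SAP 8.1 already requires Stage 1 completion, and nothing in SAP 8.10 assigns an efficacy analysis to per protocol. Its one named use, SAP 8.7, is descriptive. All of that stands and limits the consequence. A reader might infer that the primary t-test falls on an empty set; the documents do not show that, because SAP 8.10.1 names no set. The slip still has to be corrected, since 8.7 requires the tables and 8.4 refers to per-protocol analyses.

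It can also be said that the end of Stage 1 is clear enough. SAP 8.10.2.1 puts the Stage 1 endpoint at Visit 13, SAP 4.0 puts the six-month visit after completion of Stage 1 or 2, and protocol 4.1 and 9.0 separate Stage 1 from follow-up. That mostly stands. SAP 2.0 points the other way, with Stage 2 offered "after completing the six-month follow-up visit at the end of Stage 1". The set is empty on either reading, so this is a tidying matter.

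On the equivalence condition, the estimate concerned is exploratory and the SAP's own intent-to-treat rules carry no such condition. This also stands. A reader might go further and infer that the plan would report a biased estimate under the intent-to-treat label, off by the stoppers' share of an arm: 1/8 to 2/8 SD on MDMA or 1/4 to 2/4 SD on placebo, for 1 or 2 stoppers who differ by 1 SD. Protocol 12.0 does not support that. If the test passes, the stoppers are in; if it fails, no intent-to-treat estimate is described at all. Those shifts compare a completers-only mean with an all-subjects mean.

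Finally, the percentages rest on assumed stopper counts, margins and differences. They do; they show how much the unstated rule matters and predict nothing about this trial.

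**Conclusion.** The point holds, within limits. As written, the per-protocol set is 0 of 12; this follows from the text with no assumption. Protocol 12.0 conflicts with protocol 5.4 and with the SAP on whether an intent-to-treat estimate is unconditional. When the equivalence test fails, only completer-based results remain, which defeats the passage's stated aim. Under the assumptions above (2 against 10, true difference 1 SD), the chance of pooling is anywhere from 0.7% to 78.5%.

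The unnamed primary set and the mismatch between randomised or treated subjects (SAP 8.1) and enrolled subjects (SAP 8.4) are lesser points. The unnamed set should not be dismissed as harmless, because one subject with a Visit 13 score can be an eighth or a quarter of an arm.

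**What to change.** - **SAP 8.4, first limb:** change *completes* to *does not complete* and add *(Visit 13)* after the primary endpoint. Keep the second limb, on subjects found ineligible.
- **SAP 8.1, per protocol:** replace *completed Stage 1* with *completed through Visit 13*.
- **Protocol 12.0:** delete the equivalence condition and include the available data of subjects who stop before session 2, as protocol 5.4 provides.
- **SAP 8.4, intent to treat and safety:** replace *all enrolled subjects* with the Safety and ITT populations of 8.1, keeping the provision for all available data.
- **SAP 8.10.1:** name ITT (all randomised) as the primary set and per protocol as supportive. Report by arm how many randomised subjects lack a Visit 13 LSAS.

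Make these changes before the analysis and without reference to outcome data by arm. A deadline of before any unblinding may not be achievable, because each subject's blind is broken after that subject's own six-month visit.

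The cost is wording only: no added visits, data or subjects. Including stoppers can move the exploratory estimate in either direction. Deleting the condition does not supply a missing Visit 13 score; SAP 8.2 only reassigns early-termination data to a scheduled visit.

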8.5 Pooling of Investigator Centers

All subjects in this study come from one investigational center.

8.6 Baseline Values

Baseline values are from screening/baseline visit for all measures, except C-SSRS. For C-SSRS, baseline (visit 2) scores will be used as a measure of 'lifetime' suicidal ideation and behavior, and preparatory session 3 (visit 5) will be used as 'baseline.'

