5.2 Study Procedures and Visit Descriptions

5.2.1 Prescreening and Screening

The therapist team for this study will consist of the PI, [name]., and co-investigator [name]. Candidate, and all study visits will be completed at Harbor-UCLA Medical Center. Prospective subjects will be prescreened by telephone or email according to an IRB-approved script to learn if they meet basic eligibility criteria. All individuals who are prescreened should be assigned a screening number and recorded on the Subject Screening Log where information on the selection of potential subjects in the trial should be collected.

Upon signing the IRB-approved informed consent form (ICF), the potential subject may commence study-related screening activities. The screening number should also be recorded on the signed ICF. If a subject is enrolled, the study staff should record the enrollment date and assign a subject number. If a subject is not enrolled, an explanation should be recorded on the Screening Log. A CRF will not be completed for subjects who are not enrolled. These subjects will only be documented on the Screening Log and Source Records. It is the responsibility of the PI to file the Screening Log in the investigator site file (ISF) to be readily available for on-site monitoring and/or inspection by relevant authorities. Screening may take place over more than one day and should be complete by up to two months prior to enrollment. If, after reviewing all information, the PI concludes that a subject is eligible, they will enroll the subject in the study. Visits will be scheduled consecutively, as described in the Time and Events Table.

- a. Explain and obtain written informed consent from the subject and Support Partner. Written informed consent must be obtained from the subject prior to performing any tests or evaluations for the study.
- b. Assign the subject a screening number. Complete the Screening Log.
- c. Review the ability of females of childbearing potential to become pregnant and their commitment to practice appropriate birth control, as determined by the PI for the treatment period of the study.
- d. Collect perceptions about the study using the Feedback Questionnaire.
- e. Administer C-SSRS to assess suicide risk.
- f. Administer the SCID-I-RV to assess co-morbid psychological disorders.
- g. Administer ADOS-2, Module 4 to confirm autistic status.
- h. A blinded IR will administer the LSAS.
- i. Obtain medical and psychological history by interview.

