- d. The therapists will inquire about any possible changes in the subject's health to ensure that subject continues to meet eligibility criteria and, if applicable, will confirm that the subject has appropriately tapered off of medications.
- e. The subject and therapists will discuss goals for the experimental session and will review what will happen during the experimental session.
- f. During one of the preparatory sessions, the therapists will introduce the subject to the staff at the outpatient research center who they will be most likely to encounter before, during, or after treatment sessions.
- g. The Support Partner will meet with the therapists prior to the first experimental session to review and confirm their role and responsibilities and sign an ICF addendum. There must be mutual agreement between the subject and therapists concerning the presence of the Support Partner.
- h. The therapists will administer the C-SSRS just prior to beginning the second preparatory session, unless a subject is still undergoing medication washout. Subjects still undergoing medication washout will complete the C-SSRS during the second preparatory session or at a point after washout is complete prior to the first experimental session.
- i. Assess general wellbeing at each preparatory session.
- j. At the end of the first preparatory session, subjects will complete:
 - a. BDI-II
 - b. STAI
 - c. PSS
 - d. IRI

- e. RSES
- k. At the end of the second preparatory session, subjects will complete the TASIT.
- l. The second preparatory session will include a comprehensive tour of the treatment location and introductions to all available research and support personnel who subjects are likely to see during experimental sessions.
- m. At the end of the third preparatory session, subjects will complete:
 - a. ERQ
 - b. TAS-20
 - c. QoL-Q
- n. During the third and last preparatory session, give the Reminder of Study Rules to the subject, which includes instructions and restrictions for conduct prior to receiving the drug. Subjects must agree to:
 - Refrain from eating after 24:00 (midnight) the evening before the experimental session.
 - Ingest only alcohol-free liquids after 24:00 (midnight) the evening before the experimental session.
 - Refrain from the use of any psychoactive drug, with the exception of caffeine or nicotine, within 24 hours of each experimental session.

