Descriptive statistics will be computed for vital signs and subjective distress during each experimental or open-label session. The sponsor will compare pre-drug and post-drug peak blood pressure, heart rate, and body temperature during and after all experimental sessions by condition and MDMA dose. Analyses will compare peak vital signs between MDMA and placebo subjects, and a separate analysis will consider the effects of dose (0, 75, 100 or 125 mg MDMA) upon vital signs.

Frequency tables will be produced on prevalence of spontaneously reported reactions and AEs. Number and severity of spontaneously reported reactions will be compared in MDMA and placebo subjects using a one-way analysis of variance (ANOVA). The effects of MDMA dose upon number and severity of spontaneously reported reactions will also be assessed. Presence and degree of exacerbated symptoms across MDMA and placebo participant will also be examined.

Perceptions of study participation will be examined at baseline, 6-month follow-up, and end of Stage 2 using the Feedback Questionnaire and a qualitative interview. The results of this qualitative analysis will inform the sponsor of expectancies and perceptions about study procedures for future protocol development. Similarly, belief of condition assignments collected during Stage 1 will be used to assess the effectiveness of the double-blind in preparation for future studies. Results from the Feedback Questionnaire and safety data will be utilized to find the appropriate active MDMA dose for future studies.

To facilitate the planning of future studies, a preliminary estimate of effect size may be performed after all the subjects have completed the outcome assessments, one month after the second experimental session, but not all subjects have completed the six-month follow-up evaluation. This preliminary estimate will consist of safety and outcome measures. Results of the preliminary estimate will have no effect on study conduct.

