7.0 Measures

7.1 Outcome Measures

- Liebowitz Social Anxiety Scale (LSAS), total score
- Perceived Stress Scale (PSS), total score
- Beck Depression Inventory-II (BDI-II), total score
- Interpersonal Reactivity Index (IRI), composite scores
- Rosenberg Self Esteem Scale (RSES), total score
- State Trait Anxiety Index (STAI), composite scores
- The Awareness of Social Inference Test (TASIT), composite and total scores
- Toronto Alexithymia Scale 20 (TAS-20), total score
- Emotional Regulation Questionnaire (ERQ), composite scores

- Quality of Life Questionnaire (QoL-Q), composite and total scores

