Vital signs

Vital signs (heart rate, body temperature, systolic and diastolic blood pressure) will be summarized using descriptive statistics at baseline and at each post-baseline time point. Occurrences of systolic and diastolic blood pressure, heart rate, and body temperature readings above the pre-determined cutoff will be displayed with numbers and percentages by timepoint.

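### SAP 8.6 takes baseline from the screening/baseline visit, where nine of the ten outcome scales are not collected and where vital signs are not the session's pre-drug reading

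*SAP*

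**What the plan says.** SAP 8.6 gives one general rule: "Baseline values are from screening/baseline visit for all measures, except C-SSRS". The only exception is C-SSRS, where visit 2 supplies the lifetime score and preparatory session 3 (visit 5) supplies the baseline.

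SAP 8.10.2 tests change from baseline to visit 13 for all secondary measures, by the same method as the primary LSAS analysis. For vital signs, SAP 8.10.4 says that they "will be summarized using descriptive statistics at baseline and at each post-baseline time point" and does not define baseline again.

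The protocol places the first measurements at different visits. At screening (5.2.1), "A blinded IR will administer the LSAS", and blood for the baseline biomarkers is drawn. In 5.2.2, a list headed "At the end of the first preparatory session, subjects will complete" contains BDI-II, STAI, PSS, IRI and RSES. Then "At the end of the second preparatory session, subjects will complete the TASIT". ERQ, TAS-20 and QoL-Q follow at the third preparatory session. The same section explains that baseline measures are deliberately spread over the preparatory sessions to limit fatigue.

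For vital signs, protocol 12.0 says: "The sponsor will compare pre-drug and post-drug peak blood pressure, heart rate, and body temperature during and after all experimental sessions by condition".

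**The concern.** A baseline definition tells the programmer which record to subtract. Followed exactly, this one finds no record for most of the scales whose change SAP 8.10.2 tests. It also supplies no baseline TAS-20 score, which SAP 3.2 names as a possible predictor of LSAS outcome. The programmer would have to depart from the SAP without written authority.

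Vital signs are a different case, because a screening reading does exist. The rule would return a number without any visible failure, but it would be a reading from an eligibility examination and not the one taken just before dosing. Protocol 12.0 describes the trial as primarily a safety study, so the safety tables should state clearly which reading they call baseline.

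**Working it through.** No sample-size, power or alpha figure is involved. The check compares the measures named in SAP 7.1 and 7.2 with the visit columns of protocol Table 2, confirmed against protocol 5.2.1 to 5.2.3. Table 2 labels V1 and V2 as baseline and V3 to V5 as preparatory sessions. The first experimental session is V6.

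| Measure | First collected | Value at V1–V2? |
|---|---|---|
| LSAS | V2 | Yes |
| BDI-II, STAI, PSS, IRI, RSES | V3 | No (5 scales) |
| TASIT | V4 | No (1 scale) |
| ERQ, TAS-20, QoL-Q | V5 | No (3 scales) |
| OT, AVP, CORT | V2 | Yes |
| General Wellbeing | V3 | No |
| SUD | V6, pre-drug | No |
| BP, pulse, temperature | V2 physical examination; again pre-drug at V6 and V10 | Yes, but not the session reading |

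**Scales.** SAP 7.1 lists ten, beginning with "Liebowitz Social Anxiety Scale (LSAS), total score". Without a value at V1–V2: 5 + 1 + 3 = 9. With a value: 10 − 9 = 1, the LSAS. If baseline is instead the last value before the first experimental session, all 10 have one.

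**Is there any choice to make for the nine scales?** No. Each has exactly one scheduled administration before V6, so the intended baseline is that value.

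**Vital signs.** Protocol 5.2.1 puts blood pressure, pulse and temperature in the screening physical examination, which Table 2 places at V2. Four places point to the session day instead:
- Protocol 5.2.3 has all three measured at baseline before the drug is given.
- Protocol Table 4 labels the 9:45 blood pressure and pulse readings as baseline, before administration at 10:00.
- Protocol 12.0 compares pre-drug with post-drug peak values.
- SAP 3.3 describes baseline and hourly measurement during experimental sessions, until return to baseline.

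**Interval between the two readings.** Three weekly preparatory visits lie between V2 and V6. Screening itself may take up to two months (protocol 4.1). Where a medication taper applies, it starts at V3, after the screening reading. The same screening value would also serve V10, about a month after V6, and the Stage 2 sessions, which follow the visit six months after V10.

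**What uses the vital-sign baseline.** SAP 8.10.4 plans descriptive statistics by time point and counts of readings above a cutoff. It plans no change from baseline. The only planned pre/post comparison is in protocol 12.0, and it is already defined on pre-drug values.

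**The case against.** The strongest reply is that nobody would be misled. Protocol 5.2.2 has baseline measures in its heading and says that they are spread over the preparatory sessions. Each of the nine scales has a single pre-dose value, so there is nothing to choose between. This stands, and it rules out the inference that change from baseline cannot be computed for these scales. It can be, once the sentence is read with the protocol.

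It can also be argued that the C-SSRS exception does not prove a narrow reading of the general rule. C-SSRS is given at both V2 and V5 and has separate lifetime and current forms, so it needs a selection rule in any case. That is fair. Even so, the same SAP paragraph calls visit 2 baseline and visit 5 a preparatory session, so its own vocabulary separates the two kinds of visit. Stretching the general rule to cover V3 to V5 goes against that wording.

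For vital signs, Table 2 ticks the monitoring row only at V6 and V10, and the screening readings belong to an eligibility examination. A reader might infer that the acute cardiovascular and temperature results would be measured against an old reading and so compromised. The documents do not support that. SAP 8.10.4 is descriptive, and the protocol 12.0 comparison uses the session's pre-drug value. What remains is that SAP 8.6 says all measures, vital signs are a SAP 7.2 measure, and SAP 8.10.4 makes no exception.

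The SAP's own Stage 1 schedule was not legible in the text available, so its label for each visit could not be checked. Visit timing here rests on protocol Table 2, and protocol 5.2.1 to 5.2.3 agree with it.

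**Conclusion.** The concern holds as a contradiction between a stated SAP rule and the schedule. Taken literally, the rule covers 1 of 10 outcome scales, gives no baseline for SUD or General Wellbeing, and selects the screening reading for vital signs.

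The practical effect is modest. No data are lost, the intended values can be recovered from the protocol, and the primary LSAS analysis and the biomarkers are untouched because both have V2 values. For vital signs the exposure is limited to the baseline row of the SAP 8.10.4 tables and any change computed from it. The SAP should be corrected before programming, but the error does not invalidate any planned result.

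This rests on two assumptions: that the screening/baseline visit means V1–V2, as protocol Table 2 labels them, and that the SAP's Stage 1 schedule matches that table.

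**What to change.** Keep the C-SSRS sentence as it is (V2 lifetime, V5 baseline). Replace the general sentence in SAP 8.6 with text to this effect:

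- Baseline is the last value before the first experimental session: LSAS and biomarkers V2; BDI-II, STAI, PSS, IRI and RSES V3; TASIT V4; ERQ, TAS-20 and QoL-Q V5; General Wellbeing the last preparatory-session value.
- For vital signs and SUD, baseline is the pre-drug reading of the same experimental session.

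The C-SSRS rule must remain a separate exception. C-SSRS is also scored at the start of V6, and a general last-value rule would blur its baseline. The population-specific symptoms are recorded at V1 and again at V3 to V5, so the paragraph should also say which of these records counts as their baseline.

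The cost is one SAP paragraph. It needs no new visit, assessment or data collection, and it brings the SAP into line with protocol 5.2.2, 5.2.3 and 12.0.
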